10.3. Independent Ethics Committee (IEC)

It is the responsibility of the investigator to have prospective approval of the study protocol, survey, other relevant documents (for example, recruitment advertisements), and any protocol amendments, if applicable, from the individual country’s Ethics Committee (EC). All correspondence with the EC will be maintained in the Investigator File by Lilly.

Approval of this protocol by the respective local ECs will be sought prior to initiating the survey in each country.

10.4. Ethical Conduct of the Study

The study will be conducted in accordance with legal and regulatory requirements, as well as with scientific purpose, value and rigor and follow generally accepted research practices described in the *Guideline on Good Pharmacovigilance Practices (GVP) Module XVI- Risk Minimisation Measures: Selection of Tools and EMA, Good Pharmacoepidemiology Practices (GPP)* issued by the International Society for Pharmacoepidemiology (ISPE), *Good Epidemiological Practice (GEP)* guidelines issued by the International Epidemiological Association (IEA), *Good Outcomes Research Practices* issued by the International Society for Pharmacoeconomics and Outcomes Research (ISPOR), *International Ethical Guidelines for Epidemiological Research* issued by the Council for International Organisations of Medical Sciences (CIOMS), European Medicines Agency (EMA) European Network of Centres for Pharmacoepidemiology and Pharmacovigilance (ENCePP) *Guide on Methodological Standards*

**Non-Interventional Study Protocol
for Humalog 200 units/ml KwikPen
Version 1.0**

in Pharmacoepidemiology, and FDA Guidance for Industry: Good Pharmacovigilance and Pharmacoepidemiologic Assessment.

11. Management and reporting of adverse events/adverse reactions

This study does not involve data collection on clinical endpoints on individual patients.

The Internet survey does not include questions that could potentially identify a safety event, nor does it provide a free text field where study participants could specify information that may constitute a safety event (defined as an adverse event, product complaint, or other reports; e.g. overdose, abuse, misuse, off label use, pregnancy exposures, breast feeding exposures, lack of drug effect, medication error and suspected transmission of infectious disease).

However, it is possible that while in conversation with a CCA, a telephone respondent may provide information that could constitute a SE. Additionally, a participant responding by paper survey may provide information that could constitute a SE in a handwritten response on their paper survey. An AE is any undesirable medical occurrence in a patient administered a Lilly product (drug or device) and which does not necessarily have to have a causal relationship with the treatment. Trained CCAs will record any reference to a SE in temporal association with Humalog 200 units/ml as stated (verbatim) in the UBC Humalog 200 units/ml SE Form, along with the respondent's contact information, if consent to provide contact information is given. The respondent will also be informed that someone from Lilly may contact them to obtain additional information about the event. If consent is not granted, UBC personnel will report the SE with the information provided by the respondent. Information on all reports (telephone or paper) that may constitute a SE will be forwarded to Lilly as described in the Safety Event Project Specific Procedure (SE/PSP). Lilly will report all safety event information to ECs and applicable regulatory agencies as required.

Study personnel are requested to report suspected adverse reactions with Lilly drugs not under evaluation and with any non-Lilly drugs to one appropriate party to avoid duplication, (for example, regulators or Lilly) as they would in normal practice as required by applicable laws, regulations and practices.

12. Plans for disseminating and communicating study results

A final report for each stakeholder group describing the survey objectives, detailed methods, results, discussion, and conclusions will be developed at the end of the survey for submission to EMA and applicable local regulatory agencies within the timeframe specified in ‘Section 6. Milestones.’ In addition, the study results will be published on the EU PASS register.

13. References

- American Diabetes Association (ADA). Standards of medical care in diabetes—2014. *Diabetes Care*. 2014; 37 Suppl 1:S14-S80.

Annex 1. List of Standalone Documents

Number	Document reference number	Date	Title
1	Appendix I.1		Draft HCP Survey
2	Appendix I.2		Draft Survey Invitation letter for HCPs
3	Appendix I.3		Draft Patient Survey
4	Appendix I.4		Draft Survey Invitation letter for Patients
5	Appendix I.5		Direct Healthcare Professional Communication on the correct use of Humalog 200 units/ml KwikPen
6	Appendix I.6		Important Safety Information for Humalog 200 units/ml KwikPen

APPENDIX I.1 HEALTHCARE PROFESSIONAL SURVEY

SURVEY LEGEND

- **[PROGRAMMER]** is used to indicate directions to the programmer and is set in bold, red, uppercase letters between square brackets.
- **(INTERVIEWER)** is used to indicate directions to the phone interviewer and is set in bold, blue, text between parentheses. This text appears when content is to be administered by phone only (for example, spontaneous AE reporting).
- **[ONLINE]** indicates a question is worded specifically for administering the survey online.
- **[BEGIN SURVEY CONTENT]** and **[END SURVEY CONTENT]** are used to indicate to the programmer the type of survey administration and the beginning and end of the survey or sections within the survey content.
- **[TERMINATE]** is displayed next to responses that should cause the survey to end. The following termination language will be programmed into the survey or read by the interviewer.

Thank you very much for your time today. Based on your answer, you are not eligible to take this survey. We appreciate your interest in the survey.

- **[RANDOMISE LIST]** is inserted before questions to indicate to the programmer that the responses should be randomised. Responses such as “I don’t know,” “Prefer not to answer” or “None of the above” will always appear at the end of the randomised responses.
- **[GO TO Qx]** (skip logic) is inserted after a response to indicate to the programmer that the survey should skip to the indicated question (for example, **[GO TO Q17]** skips to question 17). If no skip logic is indicated the survey continues to the next question in the sequence.
- **[MULTILINE INPUT]** indicates to the programmer that multiple lines should be provided for data entry.
- **[FREE TEXT]** indicates to the programmer that one line should be provided for data entry.

SURVEY LEGEND

- **[DROP-DOWN LIST INPUT WITH COUNTRIES TABLE]** indicates to the programmer that the response should be a drop-down list containing the countries in the table below.

United Kingdom (or other comparable EU country based on product uptake)	Germany	TBD
--	---------	-----

[WELCOME PAGE]

This survey should take approximately 15 minutes to complete. If you cannot complete the survey at this time, please return when you can. Once you begin the survey you will need to answer all questions; you will not be able to access the survey again if you exit.

Thank you in advance for your participation. Please note the application will time out after 30 minutes of inactivity.

If you are ready to begin the survey at this time, please click continue. If not, click Return Later.

Please note: Do not use the browser's back button during this survey.

[END WELCOME PAGE]

16. Are you familiar with the patient communication: *IMPORTANT SAFETY INFORMATION FOR Humalog 200 units/ml KwikPen (insulin lispro)* provided by Eli Lilly and Company?

- Yes
- No **[GO TO Q18]**
- I don't know **[GO TO Q18]**

17. Did you read the patient communication: *IMPORTANT SAFETY INFORMATION FOR Humalog 200 units/ml KwikPen (insulin lispro)* provided by Eli Lilly and Company?

- Yes
- No
- I don't know

18. **[DISPLAY ONLY IN [ENTER COUNTRY THAT HAS WEBSITE]** Are you aware of the website [ENTER WEBSITE], at which patients can access the patient communication: *IMPORTANT SAFETY INFORMATION FOR Humalog 200 units/ml KwikPen (insulin lispro)*?

- Yes
- No
- I don't know

[DO NOT DISPLAY IF 0 IS SELECTED IN Q8]

[DISPLAY ONLY IN [ENTER COUNTRY THAT DOES NOT HAVE WEBSITE]
Do you or another healthcare professional at your practice provide the patient communication: *IMPORTANT SAFETY INFORMATION FOR Humalog 200 units/ml KwikPen (insulin lispro)*, to patients receiving their first prescription of Humalog 200 units/ml KwikPen?

19.

Do you or someone at your practice provide the patient communication: *IMPORTANT SAFETY INFORMATION FOR Humalog 200 units/ml KwikPen (insulin lispro)* or the website at which the communication can be accessed, to patients receiving their first prescription?

- Yes

- No
- I don't know

[DO NOT DISPLAY IF 0 IS SELECTED IN Q8]

20. Do you or another healthcare professional at your practice discuss the patient communication: *IMPORTANT SAFETY INFORMATION FOR Humalog 200 units/ml KwikPen (insulin lispro)* with patients at the time of initial prescription of Humalog 200 units/ml KwikPen?

- Yes
- No
- I don't know

[PHONE ONLY: BEGIN SAFETY EVENT]

(INTERVIEWER: Please record if respondent spontaneously reported a safety event or product complaint during the course of this interview.)

- Yes
- No **[GO TO END SAFETY EVENT SECTION]**

Enter Safety Event or Product Complaint Verbatim

[MULTILINE INPUT]

(INTERVIEWER: Refer to Project Specific Procedure for next steps.)

[END SAFETY EVENT]

21. We would like to send you [AMOUNT/TYPE] as compensation for your time and effort, but need your name and address to do so. Do you agree to provide your contact information for this purpose?

- Yes
- No **[GO TO CLOSING]**

FIRST NAME: **[FREE TEXT]**

LAST NAME: **[FREE TEXT]**

MIDDLE INITIAL: **[OPTIONAL; MUST BE 1-DIGIT ALPHA CHARACTER]**

ADDRESS: **[MULTILINE INPUT]**

CITY: **[FREE TEXT]**

COUNTRY: **[DROP-DOWN LIST INPUT WITH COUNTRIES TABLE]**

POSTAL CODE: **[FREE TEXT]**

[CLOSING]

This completes the survey. Thank you again for your participation.

[END SURVEY CONTENT]

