9.1. Study design

This study is a multi-national, observational, cross-sectional survey design. Separate surveys will be administered to HCPs involved in the treatment and management of patients with diabetes and to patients with diabetes who have been prescribed Humalog 200 units/ml KwikPen. The study has been designed and will be executed and analysed in collaboration with UBC. The surveys have been developed to enable the study objectives to be met (Section 8).

User Testing was performed on each survey with a sample of 10 HCPs and 9 patients. The User Testing procedure was designed to assess comprehension among patients regarding the words and phrases used in select survey questions and response options. User Testing also assessed the clarity of the survey questions as presented to HCPs and the interest and acceptance of the surveys among all prospective respondents, flow and ease of completing the surveys, and preferred modes of administration. Findings and recommendations from User Testing have been incorporated into the surveys.

Assessment of the additional risk minimisation measures in the participating samples will be used to determine whether the target populations are aware of and adherent to the key message themes regarding the risk of hypoglycaemia and/or hyperglycaemia attributed to medication errors or misuse associated with the administration of Humalog 200 units/ml KwikPen. All statistical analyses will be descriptive, that is, no formal hypothesis will be tested. Study endpoints are as follows:

The tools will be considered effective if the majority of respondents demonstrate they are aware of the key risks communicated.

HCPs:

- Demonstrating that they understand the key safety messages communicated in the DHPC
- Reporting that they provided the patient communication or means to access the communication to patients at the time of first Humalog 200 units/ml KwikPen prescription
- Reporting they discussed the key safety messages in the patient communication with their patients who are receiving their first prescription of Humalog 200 units/ml KwikPen

Patients:

- Demonstrating that they understand the key safety messages communicated
- Reporting that they were provided with a copy of or means to access the Humalog 200 units/ml KwikPen patient communication from their HCP at the time of initial prescription
- Reporting that they consider the key messages during administration of Humalog 200 units/ml KwikPen

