Eligible HCPs will receive an invitation letter via email if an email address is available, or a letter in the postal mail inviting them to participate in the survey. The invitation letter (Appendix I.2) will include: an overview of the rationale for the survey, information on how to access the survey online and by telephone, and a unique User Identification (ID) to ensure that the invitation is used only once.

HCPs in the applicable countries who are involved in the treatment and management of patients with diabetes will be invited to participate in the survey. The respondent population will include a mix of prescribers who have and have not prescribed Humalog 200 units/ml. The response rate will be monitored throughout the data collection period. Reminder notices will be sent via email and postal mail, and telephone calls will be made periodically to HCPs who have been invited

but not yet participated. The HCPs that complete the survey will be reimbursed for their time spent participating as governed by local laws and country regulations.

Patients:

Surveys targeting eligible patients will be administered via the Internet, which will allow respondents to participate at a time and location that is convenient for them, and by telephone, to allow participation of respondents who do not have Internet access or are not computer literate. Both modalities will offer the same survey.

Patients will be recruited via study packets that will be provided to HCPs due to privacy concerns in the EU. All HCPs who receive an invitation to participate in the HCP survey will also receive a study packet of patient invitations in the postal mail and a letter asking them to invite eligible patients to participate in the survey. The packet will contain 10 invitation letters to be distributed. The patient invitation letter (Appendix I.4) will include an overview of the rationale for the survey, information on how to access the survey online, the toll-free number for accessing the telephone survey, and a unique User ID to ensure that the invitation is used only once. The HCPs will not be asked to select specific patients based on eligibility criteria. HCPs will forward the patient invitations to their patients for whom they have prescribed Humalog 200 units/ml. In the event an HCP has prescribed Humalog 200 units/ml to more than 10 patients, the HCP will arbitrarily select 10 patients regardless of any additional eligibility criteria.

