- HCP medical specialty (for example, endocrinology, primary care)
- Number of years practicing medicine/nursing
- Number of Humalog 200 units/ml KwikPen-treated patients the HCP managed in the 12 month period preceding the survey (self-reported)

Data pertaining to evaluation of the effectiveness of the risk minimisation measures:

The survey includes questions/statements that will assess the risk understanding and behaviour of the HCPs. The understanding level and behaviours will be analysed using descriptive statistics and CIs and will be used to determine the effectiveness of the risk minimisation measures:

- Awareness of the DHPC on the correct use of Humalog 200 units/ml KwikPen
- Understanding of the key risk messages

- Self-reported practices with respect to communication of the key risk messages in clinical practice

Patients:

Screening questions:

- Agreement to participate
- Diagnosis of diabetes
- Prescribed Humalog 200 units/ml KwikPen
- 18 years or older
- Prior or current employment by Lilly, UBC, or any national medical governing body, such as but not limited to EMA, MHRA, and BfArM

Data on demographic characteristics:

- Age
- Sex
- Country
- Education status
- Length of time with diabetes
- Length of time on any insulin therapy
- Length of time on Humalog 200 units/ml KwikPen
- Length of time on Insulin used prior to Humalog 200 units/ml

Data pertaining to evaluation of the effectiveness of the risk minimisation measures:

The survey includes questions/statements that will assess the risk understanding and behaviour of patients. The understanding level and behaviours will be analysed using descriptive statistics and CIs and will be used to determine the effectiveness of the risk minimisation measures:

- Awareness of the Important Safety Information for Humalog 200 units/ml KwikPen
- Receipt of or access to the Important Safety Information
- Understanding of the key risk messages
- Patient behaviour with respect to the key risk messages

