9.9.1. Controls to minimise bias

A number of controls will be in place to ensure the survey is conducted in a professional manner and to minimise bias, including the following:

- Lists of response options will be randomised to minimise the potential for positional bias.
- The Internet and telephone surveys will be programmed to ensure that questions are asked in the appropriate sequence and all questions will be presented in a standard order to reduce exposure bias. Respondents cannot skip ahead or go back to a question once the question has been answered. All questions presented must be answered in order to complete a survey. Not all questions may be presented due to skip logic within the survey.
- Respondents will be provided with a unique code during the recruitment process and will then be asked to provide the unique code in order to gain access to the Internet-based and telephone administration systems. The code will be inactivated after use to minimise exposure bias and fraud.
- Each HCP will only be provided 10 patient packets to minimise potential over-representation bias by highly compliant HCPs (Section 9.2).

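### HCP survey Q19 and Q20 ask about first prescription, but their visible display rule does not test for one and there is no 'not applicable' answer, so the reported Yes share may be lowered

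*Protocol*

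**What the plan says.** Section 9.1 lists two HCP behaviour endpoints tied to the start of treatment. One is reporting that the patient communication, or a means to access it, was provided "to patients at the time of first Humalog 200 units/ml KwikPen prescription". The other is reporting that its key safety messages were discussed with patients receiving their first prescription.

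Appendix I.1 measures these with Q19 and Q20:

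- Q19 asks about giving the communication "to patients receiving their first prescription of Humalog 200 units/ml KwikPen". Countries with a website get a variant that also refers to first prescription.
- Q20 asks about discussing it "with patients at the time of initial prescription of Humalog 200 units/ml KwikPen".
- Both carry the rule "DO NOT DISPLAY IF 0 IS SELECTED IN Q8".
- Both offer Yes, No and I don't know, and nothing else.

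Section 9.4 lists one patient count among the HCP characteristics: "Number of Humalog 200 units/ml KwikPen-treated patients the HCP managed in the 12 month period preceding the survey (self-reported".

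Section 9.9.1 states: "All questions presented must be answered in order to complete a survey".

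Section 9.2 describes the intended sample: "The respondent population will include a mix of prescribers who have and have not prescribed Humalog 200 units/ml".

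Section 9.7 plans frequency distributions with 95% confidence intervals for every question that addresses the objectives. It fixes no separate denominator for Q19 and Q20.

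**The concern.** The display rule shows that the authors wanted to spare HCPs who have no occasion to provide or discuss the communication. On the visible text, however, it appears to test for a different event. Managing a treated patient is not the same as a patient being started at the practice. An HCP who only follows patients started elsewhere would have a non-zero count, would be shown both items, and would have to answer about something that may never have happened there.

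In the data, a No from a practice that started patients and gave them nothing would look the same as a No from a practice that started none. Two stated HCP endpoints could then mix failure to use the communication with lack of opportunity to use it. The SAP could not separate the two afterwards, because no HCP variable listed in section 9.4 records whether a first prescription took place. Section 9.4 deactivates access codes after use and section 9.6 rules out queries to respondents, so the missing information could not be collected later.

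**Working it through.** **Event asked about against event filtered on**

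| Element | Where | Refers to |
|---|---|---|
| Endpoints | Section 9.1 | First prescription |
| Q19, Q20 wording | Appendix I.1 | First or initial prescription |
| Display rule | Appendix I.1 | Q8 not equal to 0 |
| Only listed patient count | Section 9.4 | Treated patients managed, past 12 months |
| Answers offered | Appendix I.1 | Yes / No / I don't know |
| Forced answer | Section 9.9.1 | Every displayed question |

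Identifying Q8 with the count in section 9.4 is an inference. Q1 to Q15 of the HCP survey are not in the text at hand.

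**The plan's own precision**

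Equation 1 in section 9.5 gives the half-width 1.96 × √(p(1−p)/280). For p = 50, 60, 70, 80 and 90% this is 5.86, 5.74, 5.37, 4.69 and 3.51 points, which matches Table 1 (5.9, 5.7, 5.4, 4.7, 3.5). The protocol states no figure for Q19 or Q20.

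**Possible size of the bias**

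Let t be the Yes rate among HCPs whose practice had a first prescription, f the share of those shown the items whose practice had none, and y the Yes rate in that second group. All three are assumptions.

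Reported Yes share = t(1 − f) + f·y, so the shift is −f(t − y).

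With t = 80%:

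| f | y = 0 | y = 0.5 |
|---|---|---|
| 10% | 0.8 × 0.9 = 72% | 72% + 5% = 77% |
| 20% | 0.8 × 0.8 = 64% | 64% + 10% = 74% |
| 30% | 0.8 × 0.7 = 56% | 56% + 15% = 71% |
| 40% | 0.8 × 0.6 = 48% | 48% + 20% = 68% |

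The shift is downward whenever y < t. Set against Table 1's 4.7 points at 80%, it is larger at f = 10% if y = 0 (8 points). If y = 0.5 it is smaller at f = 10% (3 points) and larger at f = 20% (6 points).

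**Precision cost of excluding the 'not applicable' group**

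The Q8 rule already takes the denominator below 280. If 70% of 280 pass it (assumed), n = 196 and the half-width at 80% is 5.6 points. If 20% of those then choose 'not applicable' (assumed), n = 196 × 0.8 ≈ 157 and the half-width is 6.3 points. At 50% the change is from 7.0 to 7.8 points.

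**The case against.** The strongest objection is that the key premise rests on a question whose text cannot be read. Q8 may be worded differently from the item in section 9.4, and routing elsewhere in Q1 to Q15 cannot be checked. This stands as a limit on certainty. What remains is that the visible rule names no first prescription and that section 9.4 lists no HCP item that does.

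A reader might infer that HCPs with no first prescription are counted as failing to provide or discuss the communication. The protocol does not say so. The correct/incorrect classification in section 9.7, with I don't know generally treated as incorrect, is stated for questions on the key risk messages. Q19 and Q20 fall under self-reported practices, for which only frequency distributions are planned. These HCPs may lower the Yes share, but no rule scores them as failures.

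The wording also narrows the affected group. Q20 begins "Do you or another healthcare professional at your practice discuss the patient communication", in the present tense and covering the whole practice, and Q19 is framed in the same way. A follow-up HCP can answer Yes on behalf of a colleague, or describe usual practice. Only practices that started no patient are affected, and y may be well above zero. The Q8 rule also already removes respondents with a zero count, which limits the effect of deliberately sampling prescribers who have not prescribed the product.

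A reader might also take the 48% in the worst case as turning an effective measure into an ineffective one. The majority criterion in section 9.1 is worded for awareness of the key risks. No separate cut-off is stated for provision or discussion, and no hypothesis is tested.

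Finally, distortion of the country or specialty comparisons would require f, or the answering behaviour of this group, to differ between strata. The protocol gives no information on that.

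**Conclusion.** The point holds in limited form. The visible display rule for Q19 and Q20 does not match the event they ask about, no 'not applicable' answer exists, and an answer is forced. The denominator of the two HCP behaviour endpoints may therefore include HCPs whose practice had no first prescription, and the reported Yes share may be too low.

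The size cannot be fixed from the protocol. Under the assumed range, a true 80% would be reported between 48% and 77%. The low end needs both a large share without opportunity and no Yes answers among them; the high end has f = 10% with half of that group answering Yes. The conclusion assumes that Q8 is the managed-patient count of section 9.4.

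These endpoints serve the secondary, behavioural objective and are descriptive, so this is an inexpensive improvement to make before fielding. It is not a flaw that threatens the study's main conclusion.

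**What to change.** Add to Q19 and Q20 the response *Not applicable – no patient has received a first prescription of Humalog 200 units/ml KwikPen at my practice*. State in section 9.7 that the provision and discussion proportions are calculated among HCPs who did not choose it, and report how many chose it, so that the denominator is visible.

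The survey is still listed as a draft in Annex 1, so the change is one response option on two items and one sentence in the analysis section. The cost is a smaller denominator and slightly wider confidence intervals for these two endpoints, by less than one point in the example worked above.
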